7. METHODS

7.1 Study parameters/endpoints

7.1.1 Main study parameter/endpoint

The main outcome of this study is the feasibility of the combined procedure in terms of

- Patient tolerance: assessed with a short patient reported experience measure (PREM).
- Optimal logistics and standardization of the procedure (treatment planning, extra hospital visits).

7.1.2 Secondary study parameters/endpoints

The secondary study endpoints of this study are:

- The pain reducing capabilities of the combined treatment:
Pain scores related to the target lesion treated as measured by patient's self-assessment on a Numerical Rating Scale (NRS) in the Brief Pain Inventory (BPI) questionnaire (Cleeland 1994) post inclusion and post treatment by phone around day 3, 7, 14, 21 and 28 after the MR-HIFU treatment. The BPI is a well-established, thoroughly validated tool for pain self-assessment, which can be considered a gold standard. Patients will rate the worst and average pain that they felt from the treated area over the last three days, and the pain they feel currently.
- Safety of the combined treatment.

7.1.3 Other study parameters

Several patient and tumor related parameters will be assessed such as age, gender, primary tumor, Karnofsky performance score (KPS), location of targeted volume, number of symptomatic bone metastases, date of diagnosis of primary tumor, date of diagnosis of first symptomatic bone metastasis, prior systemic treatments received, current systemic therapy, prior radiotherapy received (including dose/fractionation schedule and dates) and MR-HIFU treatment data such as treatment duration (time in scanner, sonication time) and amount of sonifications.

7.2 Randomisation, blinding and treatment allocation

This study is a non-randomized pilot study. All eligible subjects will first receive EBRT followed by MR-HIFU. As such, there will be no blinding of the study participants and their doctors.

7.3 Study procedures

At least one day after the visit to the outpatient clinic the investigator or an authorized delegate will phone the patient to inform him/her about eligibility for the study. In case of eligibility the investigator or an authorized delegate will ask the patient for oral informed consent. If the patient is willing to participate in the study the investigator or an authorized delegate will make an appointment with the patient when the informed consent will be signed. This will preferably coincide with the patient's next visit to the hospital but latest before the preoperative screening and the MR-HIFU treatment. When written informed consent is given, the investigator or an authorized delegate will collect standard baseline demographic factors, disease history, and previous therapy for bone metastasis from participating patients and response to prior radiotherapy when applicable, as well as help the patient to fill out the BPI and record total analgesic consumption during the previous 24 hours.

Patients will be formally enrolled in the study following written informed consent, after inclusion criteria are met and none of the exclusion criteria apply. Patient screening and enrollment will be recorded on the Screening / Enrollment log. Information on withdrawal will also be recorded in this log. The Screening / Enrollment log will be used for subject accountability.

Treatment procedure

Usually single fraction EBRT is performed on the day of the patient's first visit to the outpatient clinic of the Radiation Oncology Department. The MR-HIFU treatment will be subsequently applied within the shortest time interval possible but at the latest 4 days after EBRT.

Multiple fraction EBRT is usually started within one to maximally seven days after the patient's first visit to the outpatient clinic of the Radiation Oncology Department. When multiple fraction EBRT is indicated, the MR-HIFU treatment will be minimally 3 hours and maximally 4 days after the last multiple fraction session.

Planning of MR-HIFU treatment is more challenging than planning of EBRT. Most of the time treatment planning can be done on the basis of the available (CT) images. During the MR-HIFU treatment procedure, an intravenous catheter will deliver MR contrast media and medications (such as sedation and analgesics if required) within the MR room. The need for a urinary bladder catheter is determined by the treating physician. The body temperature of the patients will be measured prior to the procedure. In the MR room the

patients will be asked to lie still on the HIFU patient table inside the MRI magnet. The operator will locate the target tissue and mark the volume to be treated using MRI images. The operator starts the treatment and monitors the progress of the treatment with MR thermal and dose maps according to the Sonalleve Instructions for Use to ensure safety. Due to the pain associated with the MR-HIFU procedure, anaesthesiologists/sedation specialists need to be involved to provide procedural sedation and analgesia. The pre-operative screening will be preferably take place on a day that the patients is already in the hospital.

Patients will receive sedation during treatment administered by an anaesthesiologist or sedation specialist. Medication given will be a combination of pain medication (e.g. rapifen) and anesthetics (e.g. propofol in combination with lidocaine for injection) at the preference of the anaesthesiologist/sedation specialist. The use of medication for treatment-related pain shall be recorded.

Following the MR-HIFU procedure, a set of MR images of the target region will be acquired with the use of a MR contrast agent. When the whole planned volume has been treated, the operator stores the full treatment history and technical data as available from the Profound Sonalleve MR-HIFU device. The patients are then conducted to the recovery room for medical supervision. Before discharge, follow-up instructions will be given to the patient.

We expect that by gaining more clinical experience with the combined treatment, we will be able to provide the combined treatment in a faster, patient-friendly way.

Follow-up

Follow up will be approximately 3, 7, 14, 21 and 28 days after the MR-HIFU treatment. The investigator or an authorized delegate will contact patients by phone to ask them whether any possible complications/adverse events have occurred. He/she will also interview the patient about their pain medication use and fill in the BPI questionnaire. At the third day after the MR-HIFU treatment the investigator will also inquire about the patient's experience with the combined treatment.

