3. STUDY DESIGN

This study will be a prospective development study (IDEAL stage 1 and 2a) (McCulloch, 2009; Verkooijen, 2017) performed at the UMC Utrecht and Isala Zwolle. A group of 6-10 patients with painful bone metastases will be studied to evaluate feasibility and logistics of the combined EBRT MR-HIFU treatment within a 3 hours - 4 day time window.

Participating doctors will be informed about the study and will be asked to inform possible eligible patients about its existence. If the patient is considered to be eligible for MR-HIFU by the treating physicians and investigators and when the patient is willing to participate, the investigator or an authorized delegate will take over and inform the patient in more detail about the study, explaining the study design and procedures and collecting informed consent and baseline data.

The inclusion preferably takes place shortly after the patient has been diagnosed and before treatment is started.

[figure not shown]
Patients who fulfil all inclusion criteria, none of the exclusion criteria, and sign an informed consent will first receive the standard of care, single or multiple fraction EBRT, followed by MR-HIFU within a 3 hours - 4 day time window.

The optimal logistic approach for administering both treatments will be assessed and protocolled. For this purpose, we will test several treatment schedules and make adjustments when needed. We will aim for the shortest time interval possible between the two treatments with a minimum interval of 3 hours and we set out to minimize additional hospital visits for participating patients.

[figure not shown]
During a follow-up period of 4 weeks, patients will be contacted by phone to retrieve information about their level of pain and pain medication around 3 days and 1, 2, 3 and 4 weeks after the MR-HIFU treatment.

A general flowchart of the study is given in the figure on the next page for both single and multiple fraction EBRT.

Single fraction EBRT

Multiple fraction EBRT

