5.2 Use of co-intervention

5.2.1 EBRT

In a first step, patients will undergo EBRT according to the standard of care on a priority base within maximally 7 days after they visit the outpatient clinic of the Department of Radiation Oncology. Patients undergo a planning CT scan, as part of standard care, in treatment position.

EBRT is provided as single fraction radiotherapy or multiple fraction radiotherapy. According to the American Society for Radiation Oncology (2012) evidence-based guidelines for the management of bone metastases, a single fraction of 8 Gray (Gy) has an equivalent pain relief quality indicator compared to longer courses of radiotherapy, including 5 or 6 fractions of 4 Gy and 10 fractions of 3 Gy (Lutz et al, 2014). However, multiple fraction radiotherapy may have a larger contribution to local tumor control and is therefore often used in patients with a longer life expectancy. The above dose fractionation schemes are recommended as quality indicators of palliative radiotherapy by the American National Quality Measures for EBRT for bone metastases. Acute and late side effects of radiotherapy for bone metastases are generally similar with single fraction versus multi fraction regimens, with some studies showing decreased acute side effects in patients receiving single-fraction radiotherapy. Time to pain relief also appears similar, with an optimal time to measure pain relief of 2 months after the completion of palliative radiotherapy.

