5.2.2 Pain medication

Subjects should receive pain medication if and as required by their symptoms, both before and after the combined EBRT and MR-HIFU treatment. The amount of pain medication used is part of the secondary endpoints of the study, and should be recorded at baseline before treatment and during the follow-up after treatment.

Pain medication used for treatment-related pain shall be noted in a separate Data Element in the CRF and in Concomitant Medication Forms. The fact that the medication was used for

treatment related pain is marked on the Concomitant Medication Forms, and the use of this medication will not be considered in the assessment of the pain response.

Patients can continue to use chemotherapy, targeted therapies (e.g. angiogenesis inhibitors) or bisphosphonates if they are already using them. The treatment type and the date the treatment was started/stopped will be recorded.

During the MR-HIFU treatment the patient will be under conscious sedation. This will enable adequate pain control and ensure a stable patient position during treatment. The sedatives used are at the preference of the anaesthesiologist/sedation specialist.

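### On the usual single-fraction path in Section 7.3, consent and the only scheduled pain baseline fall about 1–4 days after EBRT, which conflicts with the order in Section 3 and, for analgesics, with 5.2.2

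*Combined protocol and SAP*

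**What the plan says.** **Order in Section 3.** Eligible patients who "sign an informed consent will first receive the standard of care, single or multiple fraction EBRT", and then MR-HIFU. A separate sentence is softer: "The inclusion preferably takes place shortly after the patient has been diagnosed and before treatment is started".

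**Order in 7.3 and 10.2.** Section 7.3 states: "Usually single fraction EBRT is performed on the day of the patient's first visit". Both sections place the telephone call for oral consent at least one day after the first visit. Signature is preferably at the next hospital visit, and must come before pre-operative screening and MR-HIFU; no limit is tied to EBRT. The BPI and the 24-hour analgesic record are taken when written consent is given. Single-fraction patients have MR-HIFU no more than four days after EBRT.

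**EBRT timing in 5.2.1.** EBRT is given "on a priority base within maximally 7 days after they visit the outpatient clinic of the Department of Radiation Oncology". Section 7.3 starts multiple-fraction EBRT one to seven days after the visit.

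**Baseline and response.** Section 5.2.2 says the amount of pain medication "should be recorded at baseline before treatment and during the follow-up after treatment"; the sentence before it refers to the combined treatment. Section 7.1.2 schedules pain scores "post inclusion and post treatment by phone around day 3, 7, 14, 21 and 28 after the MR-HIFU treatment", so there is one BPI before follow-up, with three-day recall for worst and average pain. Section 9 uses worst pain. Its response criteria are a score of zero, a fall of at least 2 points (both with no rise in analgesics), or an analgesic reduction of at least 25% with no rise in pain. It refers to baseline and to pre-procedure medication, and does not say whether these precede EBRT or only MR-HIFU.

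**The concern.** Section 2.2 makes the pain-reducing effect of the *combined* treatment a secondary objective. A patient irradiated at the first visit and consented a day or more later has a study baseline taken after the first half of that treatment. Change from it is not change from the untreated state.

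The likelier direction of error is upward. Worst pain over three days is a maximum, so a flare on a single post-EBRT day can raise it, and the flare's resolution would then count towards response. Section 10.3 itself says MR-HIFU may prevent or reduce flare. Early relief from EBRT is a lesser worry: Section 1.2 puts adequate relief at four weeks on average, and recall on day 1 or 2 still reaches back before EBRT. Extra analgesics taken after EBRT could similarly raise the medication reference. Section 5.2.2 limits this where they are marked as taken for treatment-related pain, because then "the use of this medication will not be considered in the assessment of the pain response".

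A pre-EBRT value that nobody recorded cannot be recovered later.

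**Working it through.** The plan states no figure to reproduce. Section 4.4 makes no formal sample size calculation and Section 9 performs no tests. The check is date arithmetic, followed by an illustration.

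**1. When the baseline falls.** Let day 0 be the first visit and *e* the day of single-fraction EBRT.
- Earliest consent and BPI relative to EBRT: 1 − *e* (call on day 1 or later; 7.3, 10.2).
- Latest: (*e* + 4) − *e* = +4 (consent precedes MR-HIFU, which is within 4 days of EBRT; 7.3).

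| EBRT day *e* | Earliest | Latest | Baseline before EBRT? |
|---|---|---|---|
| 0 (usual in 7.3) | +1 | +4 | Not possible |
| 1 | 0 | +4 | Same day at best |
| 2 to 7 (allowed by 5.2.1) | −1 to −6 | +4 | Possible, not required by the visible text |

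**2. How much of the baseline is post-EBRT when *e* = 0.** For a BPI on day *d*, the share of the three-day recall after EBRT is min(*d*, 3)/3: 1/3 on day 1, 2/3 on day 2, all on days 3 and 4. The 24-hour analgesic record is essentially all post-EBRT. These are shares of time covered, not degrees of bias.

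**3. How many patients might flare.** Section 10.3 gives 2–44%. If every patient took this path (an upper bound):

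| Flare rate | Expected, n = 6 | Expected, n = 10 | At least one, n = 6 | At least one, n = 10 |
|---|---|---|---|---|
| 2% | 6 × 0.02 = 0.12 | 10 × 0.02 = 0.20 | 1 − 0.98^6 = 11.4% | 1 − 0.98^10 = 18.3% |
| 44% | 6 × 0.44 = 2.64 | 10 × 0.44 = 4.40 | 1 − 0.56^6 = 96.9% | 1 − 0.56^10 = 99.7% |

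**4. What one misclassified patient does.** 1/10 = 10 and 1/6 = 16.7 percentage points on the response rate.

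**5. Analgesics.** If the recorded baseline is 4/3 of the pre-EBRT level, a return to that level is a reduction of 1 − 1/(4/3) = 25%, which meets the third response criterion if pain has not risen.

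**6. Illustration of false response.** The inputs are assumptions, not document figures. Patient mean worst pain is N(7, SD 1.3) limited to 4–10, with daily SD 0.5 or 1.0. Baseline and follow-up are each a three-day maximum, rounded, on 0–10. There is no true effect, response is a fall of at least 2, and analgesic criteria are not modelled. Flare adds 1 or 2 points on one or all post-EBRT days. Every flare is placed inside the baseline window and none in follow-up. There were 600,000 simulated patients per cell.

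| Daily SD | No flare | 2% flare | 44% flare |
|---|---|---|---|
| 0.5 | 0.6% | 0.7–1.9% | 4.0–29.3% |
| 1.0 | 7.6% | 7.7–8.5% | 11.1–26.8% |

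Extra false responders at 2% flare: at most (1.9 − 0.6)% × 10 = 0.13. At 44%: from (4.0 − 0.6)% × 6 = 0.2 to (29.3 − 0.6)% × 10 = 2.9.

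If only half the flares fell in the baseline window, the excess would halve. At 44% and SD 0.5 the rates become 0.6 + 3.4/2 = 2.3% to 0.6 + 28.7/2 = 15%.

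**The case against.** **The same-day sentence may not govern enrolled patients.** Section 5.2.1 gives up to seven days for EBRT. Section 10.2 says these procedures are nearly always planned within a week, and justifies the one-day consideration time as letting the combined treatment be planned promptly. That reads as consent first, planning second, so the 7.3 sentence may describe routine practice. This stands as a possible reading. It adds to the need to reconcile the sections, because 7.3 sits under study procedures and a site following it would irradiate first.

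**The flowchart may give the order.** Section 3 refers to a flowchart for single- and multiple-fraction EBRT that is not visible in the text reviewed. This stands, and any statement that the plan omits the order is limited to the visible text.

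**Section 5.2.2 concerns medication only.** Correct. It does not place consent or the pain score before EBRT. For those, the conflict rests on Section 3, where only the inclusion-timing sentence is softened by a preference.

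**Other pre-EBRT data may exist.** Section 4.2 requires an NRS of at least 4 or equivalent, and Section 9 draws on medication records as well as patient report. Both may predate EBRT. The eligibility score is undated, not specified as worst pain and not named as the reference, so it helps only if the plan says how it is used.

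**The illustration overreaches if read as an estimate.** Agreed. Section 10.3 gives no onset, duration or size for flare, and the model puts every flare where it does most harm.

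**The endpoint is secondary and descriptive.** True, and stage 1 patients are reported individually. This limits the severity.

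**Conclusion.** The conflict is real but bounded. For patients given single-fraction EBRT at the first visit, the visible text puts consent and the only scheduled pain baseline about 1–4 days after EBRT, contrary to Section 3 and, for analgesics, to 5.2.2. Their response may be judged from a value EBRT has already altered. One such misclassification shifts the response rate by 10–17 percentage points. The bias itself cannot be sized from the documents: it is negligible at 2% flare, and the figures at 44% are upper-bound illustrations. Severity is minor to should-fix.

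Four stronger readings are not supported:
- *All patients are measured after EBRT.* Multiple-fraction and later single-fraction patients can be consented and measured first.
- *Section 10.2 itself puts consent after EBRT.* It supplies only the one-day minimum and otherwise suggests planning after consent.
- *The short end of the window is out of reach.* Section 3 states: "We will aim for the shortest time interval possible between the two treatments with a minimum interval of 3 hours". Consent a day or more after first-visit EBRT rules out an interval near 3 hours for that patient, but not for those irradiated later or in several fractions.
- *The study's main conclusion is at risk.* The primary measures are patient experience and logistics. The reasons in Section 1.5 for dropping the combined arm are logistics, willingness and serious adverse events. None uses the pain response.

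**What to change.** 1. Reconcile Sections 3, 5.2.1, 5.2.2, 7.3 and 10.2, and the flowchart, on the order of consent, baseline and EBRT. Say whether the same-day sentence in 7.3 applies to study patients.
2. In 7.1.2 and 9, define the response reference as worst-pain NRS and analgesic use before the first EBRT fraction.
3. Where EBRT preceded consent, use first-visit clinic values and medication records, entered after consent, if they record worst pain and medication adequately. For UMC Utrecht, state whether the PRESENT cohort holds such values; the documents do not say.
4. Otherwise flag the patient as having no pre-EBRT baseline and report that patient separately.
5. Report per patient the baseline date relative to EBRT and the EBRT to MR-HIFU interval.
6. Optionally, add a short BPI and analgesic record just before MR-HIFU and show change from it separately. This is a design preference and not needed to resolve the conflict.

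The cost is protocol wording and a few data fields; the optional record takes a few minutes while the patient is already in hospital. The downside is that some pre-EBRT values will be clinic-recorded or missing, so some of the 6–10 patients may not be classifiable for response.

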7.4 Withdrawal of individual subjects

Subjects can leave the study at any time for any reason if they wish to do so without any consequences. The investigator can decide to withdraw a subject from the study for urgent medical reasons.

7.4.1 Specific criteria for withdrawal

Patients will exit the study during the follow-up period if they have been referred to alternative palliative treatments of the treated metastasis for medical reasons (such as radiopharmaceuticals, surgery, cryotherapy or radio-frequency ablation).

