7.5 Replacement of individual subjects after withdrawal

If a subject withdraws from the study for any reason prior to MR-HIFU treatment, the subject will not count towards total enrollment and may be replaced with another subject.

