7.6 Follow-up of subjects withdrawn from treatment

Follow-up of withdrawn subjects will take place by their treating physician, according to standard clinical practice.

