8.3 Safety reporting

8.3.1 Recording of adverse events

All adverse (device) events reported spontaneously by the patient or observed by the investigator or his staff will be recorded up to 1 month after the MR-HIFU treatment.

All complications and adverse events will be documented in detail according to the latest version of the Common Toxicity Criteria for Adverse Events (CTCAE). The physicians and investigators will evaluate reported (S)AEs for determination of seriousness and causal relationship with the fact that EBRT was combined with MR-HIFU. In those instances where it cannot be determined if the event is linked to the combined treatment, this will also be noted on the patient file event report. The following aspects will be recorded for each event:

- Grade according of the AE according to the CTCAE;
- Date of onset;
- Date of recovery;
- If possible, attribution factor;
- Intervention (action taken);
- If possible, the relationship of the AE to the combined treatment.

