8.5 Follow-up of adverse events

All recorded AEs will be followed until they have abated, or until a stable situation has been reached. Depending on the event, follow up may require additional tests or medical procedures as indicated, and/or referral to the general physician or a medical specialist. SAEs need to be reported till end of study within the Netherlands, as defined in the protocol.

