9. STATISTICAL ANALYSIS

In order to reach the objectives, a two stage approach will be used following the IDEAL recommendations: IDEAL stage 1, i.e. innovation/proof of concept of EBRT followed by MR-HIFU within a 3 hours - 4 days time window, followed by IDEAL stage 2a, i.e. development of the new treatment strategy.

In the first stage, we will include three patients in whom the combined treatment will be applied and tested for the first time. In this stage, the main objective is to demonstrate the feasibility of the combined treatment strategy and describe it in detail. The report will contain clear anonymous details of the patient, exact description of the primary tumor, site of metastases, extent of the index lesion, rationale for the use of this procedure in these particular patients and a very detailed description of technical and clinical aspects of the procedures. For all patients, technical success, detailed pain scores (baseline and follow up), neurological symptoms (baseline and follow up), complications, toxicity, use of analgesics, and other relevant outcomes will be reported on an individual level. The patients reported experience will also be used to make adjustments to the logistics and treatment protocol.

After stage 1, an interval of at least two weeks will be implemented before treating the next patient to allow identification of early major problems.

Progression to stage 2a (Development) will be justified after we have demonstrated feasibility of the combined procedure, without major technical problems or safety issues. In stage 2a, the main focus is safety and technical feasibility of the combined procedure, which will be measured in 3-7 consecutive patients meeting the inclusion criteria and none of the exclusion criteria.

For all patients, we will report toxicity and pain response. The patient-reported worst pain will be used. This is consistent with the latest version of the International Consensus for clinical trial endpoints on bone pain palliation with radiotherapy.

Pain responders are defined as patients with:

1. Pain score (numerical rating scale; NRS) at the treated site of zero without analgesic increase (complete response);
2. Reduction of pain score of at least 2 points at the treated site without analgesic increase (partial response);
3. Analgesic reduction of 25% or more without increase in pain (partial response).

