11.5 Temporary halt and (prematurely) end of study report

The investigator/sponsor will notify the accredited METC of the end of the study within a period of 8 weeks. The end of the study is defined as the last patient's last follow-up moment 4 weeks after MR-HIFU.

The investigator will notify the METC immediately of a temporary halt of the study, including the reason of such an action.

In case the study is ended prematurely, the sponsor will notify the accredited METC within 15 days, including the reasons for the premature termination.

Within one year after the end of the study, the investigator/sponsor will submit a final study report with the results of the study, including any publications/abstracts of the study, to the accredited METC.

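### Referral to another treatment of the treated metastasis ends study participation, so the remaining follow-up calls stop although all study treatment has already been given

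*Combined protocol and SAP*

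**What the plan says.** Section 7.4.1 of the protocol sets one specific withdrawal criterion: "Patients will exit the study during the follow-up period if they have been referred to alternative palliative treatments of the treated metastasis". The referral must be for medical reasons; the examples are radiopharmaceuticals, surgery, cryotherapy and radio-frequency ablation. Section 7.6 adds: "Follow-up of withdrawn subjects will take place by their treating physician, according to standard clinical practice".

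The calls affected are those in Section 7.3, at about days 3, 7, 14, 21 and 28 after MR-HIFU. In them the investigator or a delegate "will contact patients by phone to ask them whether any possible complications/adverse events have occurred", asks about pain medication and completes the BPI. The patient-experience questions are asked at day 3 only.

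Other safety duties run in parallel. Under Section 8.3.1, events "reported spontaneously by the patient or observed by the investigator or his staff will be recorded up to 1 month after the MR-HIFU treatment". Section 8.5 follows events already recorded until they resolve or stabilise, and says that "SAEs need to be reported till end of study within the Netherlands". Section 11.5 defines the end of study by the last patient's "last follow-up moment 4 weeks after MR-HIFU".

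On who counts, Section 7.5 says: "If a subject withdraws from the study for any reason prior to MR-HIFU treatment, the subject will not count towards total enrollment". It has no matching rule for exits after MR-HIFU. Section 9 says: "For all patients, we will report toxicity and pain response". It also promises to report withdrawals.

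**The concern.** An exit rule makes sense when a patient must stop a study treatment. Here EBRT and the single MR-HIFU session are both complete before follow-up starts, so the rule can end only observation. The trigger is the referral, not the start of the new treatment. Calls would therefore stop while the pain scores still describe EBRT plus MR-HIFU alone.

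The exit may also depend on outcome. The text gives only medical reasons, but poor relief or a local problem are plausible ones. The record would then be shortest in patients who did less well.

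This matters because Section 10.3 says there are no data on complications of the two treatments given within 4 days of each other. The scheduled calls are the plan's only active questioning about new events. Section 7.7 makes a clearly raised complication rate, not restricted to serious events, a ground for ending the study. Duration of relief and medication use are secondary objectives (Section 2.2), and both need the later calls.

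**Working it through.** **Does the rule stop the calls?** No sentence says so directly; it is inferred from three things.
- Section 7.4.1 takes the patient out of the study, not merely out of one assessment.
- Section 7.6 hands withdrawn patients to standard care.
- No section provides for study calls after exit.

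**What remains after an exit?**
- Spontaneously reported or staff-observed events are recorded to 1 month (8.3.1), with no stated exception for exited patients.
- Events already recorded are followed until they resolve or stabilise (8.5).
- SAEs are reported to the end of study (8.5, 11.5).
- The patient appears to stay in the denominator, because 7.5 excludes only withdrawals before MR-HIFU and Section 9 reports on all patients.

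What is lost is active questioning about new events, plus later pain and medication data.

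**How much is lost per exit?** Inputs: five calls per patient at days 3, 7, 14, 21 and 28 (7.3) and a sample of 6 to 10 (4.4). The sample size has no formal calculation behind it, so there is no planned figure to reproduce.

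Total scheduled calls: 6 × 5 = 30; 10 × 5 = 50.

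| Exit after call at | Calls lost | Days without active questioning | Share of all calls, n = 10 to n = 6 |
|---|---|---|---|
| Day 3 | 4 of 5 | 28 − 3 = 25 | 4/50 = 8.0% to 4/30 = 13.3% |
| Day 7 | 3 of 5 | 28 − 7 = 21 | 3/50 = 6.0% to 3/30 = 10.0% |
| Day 14 | 2 of 5 | 28 − 14 = 14 | 2/50 = 4.0% to 2/30 = 6.7% |
| Day 21 | 1 of 5 | 28 − 21 = 7 | 1/50 = 2.0% to 1/30 = 3.3% |

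In stage 1, with three patients reported individually and then assessed by the safety committee, there are 3 × 5 = 15 calls. One exit after day 3 would remove 4/15 = 26.7% of them. At day 28, one exit leaves 1/10 = 10% to 1/6 = 16.7% of patients without data.

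**How likely is an exit?** The documents give no rate. Assuming a chance p per patient, the probability of at least one exit is 1 − (1 − p)^n:

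| Assumed p | n = 6 | n = 10 |
|---|---|---|
| 5% | 26.5% | 40.1% |
| 10% | 46.9% | 65.1% |
| 20% | 73.8% | 89.3% |

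These values of p are assumptions only. Section 1.2 says EBRT takes four weeks on average to give adequate relief, so early referral for poor relief may be uncommon.

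**How much adverse event information would be lost?** Section 12.2 reports that minor events in the MR-HIFU literature it presents subsided within 10 days. If the combination behaved the same way, which is an assumption, an exit after the day 14 call would lose little of it. The exposed cases are exits after day 3 or day 7.

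**The case against.** The strongest reply is that this is a reasonable choice in a small descriptive series. A new local treatment confounds pain scores, the patients are often frail, and the Summary names regular phone contact as part of the burden. No tests are planned, so no error rate or power is affected. The patient-experience measure is taken at day 3.

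Much safety cover also survives. If a local problem prompted the referral, it has probably been recorded already and will be followed to resolution under 8.5. Withdrawal information goes into the screening and enrolment log (7.3). Stage 1 outcomes are reported patient by patient, the investigators monitor safety continuously, and a safety committee reviews the first three patients (8.6). The adverse event gap is therefore narrow: a new, non-serious event that arises after exit and is neither volunteered nor seen by staff. No stopping condition in 7.7 has been shown to fail because of the rule.

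These points hold and keep the concern small, but they do not restore the calls. Confounding is a reason to label later pain scores, not to leave them uncollected. It does not apply between referral and the start of the new treatment, although the documents do not say how long that interval would be. Nor is it a reason to stop asking about adverse events. The log entry does not specify a referral date, a reason or a treatment start date.

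**Conclusion.** The concern holds, as a minor point. Followed as written, the rule ends the scheduled collection of pain and medication data and the active questioning about new adverse events, after all study treatment has been given and possibly in patients with worse outcomes. For one exit the loss ranges from 1 to 4 of that patient's 5 calls, or 2% to 13.3% of all scheduled calls depending on timing and sample size; an exit before the day 3 call would lose all 5.

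The conclusion rests on reading study exit together with Section 7.6 as ending the calls. The link between exit and outcome is plausible but not stated. How often exits would occur is unknown. The primary outcome is largely unaffected unless the exit precedes the day 3 call. Serious events from the combination, the safety ground in Section 1.5 for leaving it out of FURTHER, remain reportable.

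**What to change.** Reword Sections 7.4.1 and 7.6 so that referral is an event to record and not an exit from the study:
- record the date of and reason for the referral, and the date the new treatment starts;
- continue the scheduled calls to day 28 for adverse events, pain and medication, unless the patient withdraws consent.

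In Section 9, report pain scores after the referral separately from those before it, and mark those obtained after the new treatment starts. List each such patient individually among all patients treated with MR-HIFU.

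The cost is protocol wording, with notification to the METC if it is made as an amendment (11.3), and a few calls to patients under other care. The calls are already scheduled; no visits, procedures or patients are added. The choice of further treatment is untouched.
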